Analyses for the pilot validation will include: 1) comparison of categorical classifications of tympanogram types for the commercial vs prototype devices; 2) evaluating potential intra-participant correlation between ears; 3) assessing differences in numerical measures between the commercial and prototype tympanometer; and 4) evaluating performance of mHealth tympanometer and commercial tympanometer.

- 1) For each device, commercial and prototype, tympanograms will be categorized into one of 3 categories: A, B and C. To assess the agreement between the two devices with respect to categories, Bowker's test of symmetry and the Kappa coefficient conventional methods to assess agreement, will be used. For the initial analysis, both tympanograms will be performed for each ear and no adjustments will be made for participants (i.e., most will have both ears included).
- 2) To assess the potential effect of participant and ear status (normal, diseased) for participants where both ears are included, each participant's ears will be characterized as (both normal, both diseased, one diseased and one normal). Within those categories, the number of ears for which there is concordance between the two tympanograms for each participant will be 0, 1 or 2. Pearson's chi-square test will be used to compare the three groups defined by ear status with respect to the distributions of the number of ears with concordance.
- 3) The Wilcoxon signed rank test will be used to determine if the differences in the numerical measures (ear canal volume, static admittance and tympanometric peak pressure) obtained from the commercial and prototype devices are significantly different from zero. No adjustment for multiple testing is planned.
- 4) Audiologist assessment of the mHealth and commercial tympanometers will be captured through questionnaires which assess 4 performance measures using a 5-point Likert scale. For each performance measure, the Kappa coefficient and Bowker's test of symmetry will be used to assess agreement between the two mHealth and commercial tympanometers with respect to responses.

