A minimum of 30 participants will be enrolled. Both ears will be used for each patient enrolled, with enrollment remaining open until 60 ears (40 adult and 20 pediatric ears) are accrued to ensure that there are sufficient number of ears for analysis. It is possible that more than 30 participants will be required to accrue 60 ears if we are unable to obtain a tracing on one or both ears in certain patients (such as due to a draining ear, which inhibits formation of a seal). We anticipate consenting no more than 40 individuals to reach the enrollment goal of 30 participants. With a sample size of 30 participants (60 ears), a null hypothesis where kappa is 0 (no correlation between devices) can be tested against the alternative hypothesis of kappa of 0.3 using a two-sided 0.05 significance level with a power of 0.89.

Title: "Pilot Validation of a Prototype Mobile Health Tympanometer"
PI: [name], MPH
Institution: University of Arkansas for Medical Sciences

Machine Learning Algorithm Analysis

The categorizations of the tympanogram (Type A, B, C) classified by the algorithm will be compared with the audiologists' interpretations. To assess agreement between the audiologist and the algorithm, Kappa analysis and Bowker's test of symmetry will be performed.

Ethical Considerations

This study will be conducted in accordance with all applicable government regulations and UAMS research policies and procedures. This protocol and any amendments will be submitted and approved by the IRB as required.

For recruitment and eligibility determination, a partial HIPAA waiver will be obtained. PHI access under the partial HIPAA waiver will entail using the clinic schedule to screen for potential participants by their age and reason for visit. Reason for visit will be used to determine middle ear status and whether tympanometry is likely to be performed as part of the clinical visit.

For eligible participants and parents/guardian of eligible children, informed consent using IRB-approved consent materials, will be obtained before the participant begins any study procedures and will be performed electronically using a secure REDCap database. All participants for this study will be provided an electronic informed consent form (e-consent) describing this study in language understandable to the study population.

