### 2.2 Power and Sample size

A sample size of 30 participants (60 ears), with an assumed prevalence of 0.20 will yield a half-width of 95% confidence interval ranging from 0.25-0.33 when the sample sensitivity is 0.80; and a half-width of 95% confidence interval ranging from 0.12-0.18 when the sample specificity is 0.80. The range of the half-width of 95% confidence interval reflect the extreme scenario of the intra-class correlation ranging from 0 to 1.

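### Protocol analysis 2 is announced as an evaluation of between-ear correlation, but its chi-square test compares concordance by ear status and cannot show that correlation

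*Protocol*

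**What the plan says.** The opening list of the Protocol's Pilot Validation Analysis gives the purpose of the second analysis as "evaluating potential intra-participant correlation between ears". The numbered detail words it differently: "To assess the potential effect of participant and ear status (normal, diseased) for participants where both ears are included". Each such participant's "ears will be characterized as (both normal, both diseased, one diseased and one normal"), and "the number of ears for which there is concordance between the two tympanograms for each participant will be 0, 1 or 2". The test applied is Pearson's, as follows: "chi-square test will be used to compare the three groups defined by ear status with respect to the distributions of the number of ears" that are concordant on the two devices. No correlation coefficient is named as an output and no exact alternative is given. Item 2 does not say whether normal and diseased are judged by the commercial tympanogram, the prototype or otoscopy.

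On numbers, the Protocol states "A minimum of 30 participants will be enrolled" and keeps enrolment open until 60 ears are accrued.

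The SAP contains no such chi-square test and does not say that it is withdrawn. Section 2.2 sizes the study "with an assumed prevalence of 0.20" and lets the intra-class correlation run from 0 to 1. Section 5.3 estimates sensitivity and specificity by GEE with a sandwich variance. For the audiologist-versus-algorithm comparison it uses Durkalski's clustered McNemar test and a cluster-bootstrap kappa.

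**The concern.** The announced question and the test do not match. A between-ear correlation is about whether a participant's two ears tend to be concordant or discordant together. The chi-square asks whether the distribution of 0, 1 or 2 concordant ears differs between three status groups. Strong between-ear correlation that is the same in every group leaves that null hypothesis true. A difference in accuracy between normal and diseased ears makes it false even when a participant's ears are independent given their status.

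What is at stake is the interpretation of this one Protocol analysis and its consistency with the SAP. The study would carry out an analysis labelled as an assessment of correlation and come away with no estimate of it. That estimate would be useful for the larger validation study this pilot is meant to support, because the SAP's own precision statement has to span the whole range from 0 to 1.

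**Working it through.** **Stated figure.** Neither document gives a power or sample-size figure for item 2. The Protocol's only power figure, 0.89 for kappa 0 against 0.3 with 60 ears, is for a different test. It reproduces at 0.895 with three equally frequent types and ears treated as independent, and is not in dispute here.

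**Inputs from the documents.** 60 ears, so at most 60/2 = 30 participants with both ears; prevalence 0.20 and sensitivity and specificity 0.80 (SAP 2.2); two-sided alpha 0.05 (SAP 5.1). If the 20 pediatric ears came one each from 20 children, only the 20 adults would be bilateral, so the range is roughly 20 to 30.

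**Assumed, not in the documents.** Between-ear disease correlation 0.5; ear-level concordance 0.80, borrowed from the SAP's 0.80; the strengths of between-ear concordance correlation tried.

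**1. What the null hypothesis says.** With concordance c and between-ear correlation r, the probabilities of 0, 1 and 2 concordant ears are (1−c)² + r·c(1−c), 2c(1−c)(1−r) and c² + r·c(1−c).

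- c = 0.80, r = 0: 0.04, 0.32, 0.64
- c = 0.80, r = 0.5: 0.12, 0.16, 0.72
- c = 0.80, r = 0.9: 0.184, 0.032, 0.784

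If c and r are the same in the three status groups, the three rows are identical and the null is true, whatever r is.

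Now take r = 0 within every group, with concordance 0.95 in normal and 0.70 in diseased ears:

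- both normal: 0.0025, 0.095, 0.9025
- mixed: 0.05×0.30 = 0.015; 0.95×0.30 + 0.05×0.70 = 0.32; 0.95×0.70 = 0.665
- both diseased: 0.09, 0.42, 0.49

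The rows differ, so the null is false although the ears are independent given status.

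**2. Group sizes and expected counts at N = 30.** P(both diseased) = 0.20² + 0.5×0.20×0.80 = 0.12. P(both normal) = 0.80² + 0.08 = 0.72. P(mixed) = 0.16. Group sizes are 3.6, 21.6 and 4.8. Multiplying by 0.04, 0.32 and 0.64 gives:

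| Ear status | 0 concordant | 1 | 2 |
|---|---|---|---|
| Both normal (21.6) | 0.86 | 6.91 | 13.82 |
| Mixed (4.8) | 0.19 | 1.54 | 3.07 |
| Both diseased (3.6) | 0.14 | 1.15 | 2.30 |

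Seven of nine cells are below 5 and three are below 1. Over prevalence 0.2 to 0.5, concordance 0.6 to 0.9 and correlation of concordance 0 to 0.5, six to eight cells are below 5. Enumerating every set of margins at N = 30 with no empty row or column shows that at least five of nine are always below 5. Perfectly balanced margins give 30/9 = 3.33 in every cell.

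**3. Simulated rejection rates**, N = 30, nominal 0.05, latent-normal correlation between ears:

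| Scenario | Rejects |
|---|---|
| Concordance 0.80 everywhere, no ear correlation | 6.2% |
| Same, latent ear correlation 0.80 | 6.5% |
| Same, latent ear correlation 0.95 | about 7% (6.7% to 8.2% in repeat simulations) |
| No ear correlation given status, sensitivity 0.70, specificity 0.95 | 55% |

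A different correlation model agrees. With concordance 0.80 in all groups, rejection is 3.5% to 6.7% across intra-class correlations of 0, 0.5 and 0.9 and several status mixes. With zero correlation given status but concordance 0.95 in normal and 0.50 in diseased ears, it is 68% to 78%.

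**4. Correlation present in the 55% scenario.** Shared disease status induces a little marginal correlation. Overall concordance is 0.80×0.95 + 0.20×0.70 = 0.90, with variance 0.90×0.10 = 0.09. The between-ear covariance is (0.95−0.70)² × 0.08 = 0.005, so the correlation is 0.005/0.09 = 0.056. The test rejects more than half the time at a correlation of about 0.06, and about 7% of the time when the correlation is very strong but unrelated to status.

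**The case against.** The case for leaving this alone has four parts.

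- **The mismatch is mainly with the label in the opening list.** The detailed item names ear status, and the test does address it. This stands, but the detail also names an effect of participant, and the announced purpose is correlation; neither is answered.
- **The SAP has moved on.** It omits the chi-square and handles clustering with GEE, Durkalski's test and a cluster bootstrap. This stands, and it confines the point to the Protocol analysis and to Protocol/SAP consistency. A reader might infer from item 2 that the plan ignores clustering; the SAP does not support that.
- **No harm to the kappa is shown.** A reader might infer that a non-significant item 2 would license item 1's unadjusted kappa, or that a significant one would be taken as proof of correlation. The Protocol calls that kappa an initial analysis and does not make it depend on item 2, and the SAP adjusts regardless. That chain is inference, not something the documents say.
- **Sparsity does little damage.** Most expected counts are below 5, but simulated type I error stays near 5%. A reader might infer that the p-value would be badly wrong; the simulations do not bear that out. Sparsity is the secondary part of the point.

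It is also fair that a correlation from 30 pairs is imprecise. Its simulated standard deviation is about 0.16 to 0.21, so a 95% interval would span roughly ±0.3 to ±0.4. That is a reason to report the interval and its width, not a reason to keep a test of a different hypothesis.

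**Conclusion.** The point holds in a limited form. As written, Protocol analysis 2 tests whether device concordance differs by ear status. It does not estimate between-ear correlation, and at about 30 bilateral participants it rejects in about 6% to 7% of trials even when that correlation is very strong and accuracy is equal. The logical mismatch follows from the null hypothesis and needs no assumed input. The rejection rates rest on the SAP's prevalence of 0.20 and on the assumed disease correlation and concordance. Recruitment favours pathology, so the true status mix may be more balanced; the conclusion was the same at prevalence 0.5 and with equal groups.

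No SAP primary estimate, interval or sample size changes. This should be corrected because the stated question goes unanswered and the correction is cheap.

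**What to change.** In participants with both ears complete, report the within-participant correlation of concordance (intraclass or phi coefficient) with a participant-level bootstrap 95% interval. State in advance that the interval will be wide at about 30 pairs. State also that the chi-square result will not be used as evidence for or against independence of ears.

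If the ear-status comparison is kept, label it only as that. Say how status is defined: for example, by commercial tympanogram type, as in the SAP's normal-versus-diseased reference split, or by the otoscopy findings recorded by ear. Use the exact Fisher-Freeman-Halton test, since most expected counts are below 5. If it is not wanted, delete item 2 and bring the Protocol into line with the SAP.

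The cost is a wording change in the Protocol, one line in the SAP and trivial programming. No new data and no change in sample size are needed.

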**Hypothesis 1:**

The diagnostic accuracy (sensitivity and specificity) of the prototype device based on audiologist's interpretation as compared to the commercial tympanometer based on audiologist's interpretation is 80% or greater.

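### The protocol's only powered hypothesis (kappa 0 against 0.3) tests better-than-chance agreement; it does not address Aim 1 and is not reconciled with the SAP's 80% target

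*Protocol*

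**What the plan says.** **Protocol.** Aim 1 is a pilot evaluation of accuracy and performance against a commercial tympanometer. Under Data Analysis, Pilot Validation Analysis, item 1, "tympanograms will be categorized into one of 3 categories: A, B and C", and for the device comparison "Bowker's test of symmetry and the Kappa coefficient conventional methods to assess agreement, will be used". The same item says that the initial analysis makes no adjustment for participants who contribute both ears. The sample-size paragraph then takes 60 ears from 30 participants and states that "a null hypothesis where kappa is 0 (no correlation between devices) can be tested against the alternative hypothesis of kappa of 0.3". The power it gives for this is 0.89, at a two-sided level of 0.05. Item 3 adds signed rank tests on the numerical measures. No other hypothesis in the protocol has a stated null, alternative and power.

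**SAP.** Hypothesis 1 (section 1.3) is that the sensitivity and specificity of the prototype "as compared to the commercial tympanometer based on audiologist's interpretation is 80% or greater". Section 2.2 justifies the sample size by 95% interval half-widths at prevalence 0.20: 0.25-0.33 for sensitivity and 0.12-0.18 for specificity, from uncorrelated to fully correlated ears. Section 5.3 estimates both by GEE with robust variance on A versus B/C. It plans a kappa, with a cluster-bootstrap interval, only for audiologist against algorithm. It neither carries forward nor withdraws the protocol's kappa for prototype against commercial device.

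**The concern.** The two devices measure the same ear in one visit and are read by the same audiologist. Under kappa = 0 the prototype's classification would agree with the reference no more often than chance. Rejecting that null is a low bar: it does not show that the prototype is accurate, or how accurate it is.

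The two documents therefore attach different criteria to one comparison, and neither explains how they relate. The protocol plans to use these data to support a larger grant application. A significant kappa reported beside a power of 0.89 could be read there as more than it is, especially if ears are treated as independent.

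**Working it through.** **1. Reproduce the stated power.** Use the large-sample test for Cohen's kappa: power = Φ[(κ₁√n − 1.96 s₀)/s₁]. Here s₀ = √(pe + pe² − Σ rᵢcᵢ(rᵢ + cᵢ))/(1 − pe), with rᵢ and cᵢ the marginal proportions, and s₁ is the corresponding standard error under the alternative. From the protocol: κ₁ = 0.3, n = 60, two-sided 0.05. The marginals are not given, so they are assumed.

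- Three equal categories: pe = 1/3, s₀ = 0.707, s₁ = 0.748; power = Φ[(2.324 − 1.386)/0.748] = Φ(1.25) = 0.895.
- 0.4/0.3/0.3: 0.892. 0.5/0.25/0.25: 0.880.
- 0.8/0.1/0.1: 0.784. Two categories: 0.63-0.65.

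So 0.89 reproduces for three roughly balanced types and 60 independent ears. The figure is not in dispute. With three equal categories, the alternative of 0.3 means raw agreement of 1/3 + 0.3 × 2/3 = 0.53.

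**2. How often would a prototype below 80% reject kappa = 0?** Prevalence 0.20 is from SAP 2.2, and independent ears match the protocol's unadjusted analysis. The values Se = Sp = 0.70 and 0.75 are assumptions.

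Binary kappa at 0.70: po = 0.70; positive-call rate = 0.20 × 0.70 + 0.80 × 0.30 = 0.38; pe = 0.20 × 0.38 + 0.80 × 0.62 = 0.572; κ = 0.128/0.428 = 0.299. At 0.75: po = 0.75, pe = 0.590, κ = 0.160/0.410 = 0.390.

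For the three-type scale I split diseased ears equally between B and C and split false positives equally. I then let the share of detected ears given the correct type (B or C) be 1.0, 0.8 or 0.5. Rejection rates are simulated.

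| Se = Sp | Binary κ | Rejects | Three-type κ (share 1.0 / 0.8 / 0.5) | Rejects |
|---|---|---|---|---|
| 0.70 | 0.299 | 0.73 | 0.356 / 0.296 / 0.206 | 0.94 / 0.87 / 0.62 |
| 0.75 | 0.390 | 0.90 | 0.438 / 0.371 / 0.270 | 0.98 / 0.95 / 0.82 |

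**3. Sensitivity to the assumed inputs (binary scale).**

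- Prevalence 0.20: 0.60/0.60 rejects about 25% of the time, 0.65/0.65 48%, 0.79/0.79 97%, and Se 0.50 with Sp 0.80 56%.
- Se = Sp = 0.70-0.75: about 50-71% at prevalence 0.10 and 89-98% at 0.50.

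**4. Effect of ignoring pairing.** If the two ears of each participant were fully correlated and analysed as 60 independent ears (binary, prevalence 0.20), 0.70-0.75 would reject 67-82% of the time. Type I error would be about 18% instead of 5%. This is the extreme case.

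**The case against.** The strongest reply is that this is a pilot, the SAP's stated objective is preliminary estimation, and the SAP already does most of what is asked. Its primary device analysis is sensitivity and specificity with clustering handled, and its sample size rests on precision. That stands, and it confines the point to the protocol's kappa statement and unadjusted device kappa.

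Four stronger readings are tempting, and the documents do not support them.

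- A reader might infer that kappa = 0 is the protocol's only test of the device comparison. It is not: Bowker's test and the signed rank tests are also named. It is the only hypothesis with a stated power. The others test symmetry and shift, so they do not address the 80% target either.
- A reader might infer that a significant kappa would count as validation. Neither document says so or gives a decision rule.
- A reader might infer that 73-90% describes failing prototypes in general. It describes the inputs chosen above; step 3 shows a much wider range.
- A reader might infer that kappa = 0.3 is by definition a device that fails Hypothesis 1. That follows only on the binary scale at prevalence 0.20. The protocol's kappa has three categories. With B and C confused at random, a device exactly at 80%/80% has κ = (0.533 − 0.333)/0.667 = 0.30 for equal categories, and (0.72 − 0.576)/0.424 = 0.34 for 0.8/0.1/0.1. A binary kappa should therefore not serve as a pass mark for the three-type kappa.

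**Conclusion.** The point holds as a mismatch between the protocol's powered hypothesis and the study's question. Kappa = 0 against 0.3 tests better-than-chance agreement, does not address Aim 1, and is left unreconciled with the SAP's 80% target and precision-based sample size. The stated power is reproducible and is not the problem.

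The illustrative size, 73-90% rejection on the binary scale and 62-98% on the three-type scale, depends on Se = Sp = 0.70-0.75, prevalence 0.20 and 60 independent ears. The three-type range also depends on how often B and C are confused. The consequence reaches the protocol's power statement and its unadjusted device kappa, not the SAP's primary conclusion. It should be corrected, and the correction is cheap.

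**What to change.** In the protocol's sample-size paragraph, replace the kappa 0 against 0.3 statement with the SAP's basis: sensitivity and specificity with 95% intervals and the half-widths of SAP 2.2. Name the interval method when carrying these over. The SAP does not name it, and a simple Wald calculation, 1.96√(0.16/m), gives 0.23 (m = 12) to 0.32 (m = 6) and 0.11 (m = 48) to 0.16 (m = 24), slightly narrower than printed.

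In item 1 of the Pilot Validation Analysis, report the device kappa as an estimate with a 95% interval that respects two ears per participant, in place of the unadjusted test. The cluster bootstrap in SAP 5.3 would serve; add the device kappa there. State that rejecting kappa = 0 is not evidence of adequate agreement. If a kappa precision is quoted, about 0.24 (independent ears) to 0.35 (fully correlated) applies at Se = Sp = 0.80 and prevalence 0.20, and must be labelled A versus B/C.

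A formal test against 80% would not be a workable substitute. About 60 × 0.20 = 12 diseased ears are expected, and even 12 of 12 detected has probability 0.8¹² = 0.069 when true sensitivity is 0.80.

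The cost is wording in both documents and one added interval, with no extra participants. The drawback is that a high-power statement gives way to a precision statement that looks less favourable.

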## Activity Log

---

### Acronyms

AC	Arkansas Children's
CI	Confidence interval
CNE	Could not evaluate
ECV	Ear Canal Volume
FDA	United States Food and Drug Administration
IRB	Institutional Review Board
ITT	Intent-to-Treat
IQR	Interquartile range
LOA	Limits of Agreement
LMICs	Low- and middle-income countries
mHealth	Mobile Health
ML	Machine Learning
PP	Per Protocol
REDCap	Research Electronic Data Capture
SA	Static Admittance
SAP	Statistical Analysis Plan
SD	Standard deviation
TPP	Tympanometric Peak Pressure
UAMS	University of Arkansas for Medical Sciences

---

Target Journal(s):

ClinicalTrials.gov number/link:

## 1 Study Overview

### 1.1 *Background/Introduction:*

The goal of the “Statistical Analysis Plan” (SAP) outlined here is to provide a comprehensive document that provides required details for the summary, visualization, and analysis of the data that is measured and/or observed during the course of the study “Pilot Validation of a Prototype Mobile Health Tympanometer”. This SAP is finalized based on the study protocol finalized on 03/07/2024.

The protocol should be read with the understanding that the outlined methods related to summarizing, displaying, and analyzing the study data should be considered flexible, and deviations from the pre-planned approach may be required. Statistical analyses rely on satisfactorily meeting different assumptions that can be validated only during data analysis. Hence deviations from the pre-planned analysis approach can be inevitable. A statistical and/or clinical description justifying the need for these deviations will be included.

An estimated 1.6 billion people are living with hearing loss globally, making hearing loss the second leading impairment worldwide. Unfortunately, over 80% of affected individuals reside in low- and middle-income countries (LMICs) with limited access to hearing care. To be effective, screening must account for the type and prevalence of hearing loss in a given population. Most screening programs only use pure-tone screening and are not equipped to identify middle ear disease that is widespread in populations with a high prevalence of infection-related hearing loss. A major reason for this gap is that tympanometry, the device used to clinically identify middle ear disease, is not typically used for screening because it is expensive and designed to be operated by trained professionals. To address the barriers of cost and training, the study team has developed a low-cost, lay-friendly mobile health (mHealth) tympanometer and a novel machine learning (ML) algorithm that together simplify detection of middle-ear disease and interpretation of results. The new device has the potential to transform hearing screening in LMICs, where the burden of hearing loss is greatest and is not addressed by current hearing screening methodology.

To prepare the new device for large-scale testing by lay-screener, the device needs to be validated. This study represents a first-in-human pilot validation with audiologists that will compare the performance of the prototype to a commercially available tympanometer in 60 ears (approximately 20 adults and 10 children). This study will also evaluate the performance of the ML algorithm using data from the prototype tympanometer. This early feasibility study of the mHealth tympanometer will be conducted in partnership with audiologists at the Audiology Clinics of the University of Arkansas for Medical Sciences (UAMS) and Arkansas Children’s (AC). Information from this study will guide design modifications in the device for large-scale validation studies needed to bring this evidence-based technology to underserved communities in the rural US and abroad.

